5.2 Analysis Methods

The following section defines hypothesis that will be tested. However, given the feasibility nature of the study no acceptance criteria were defined and estimating absolute effects and statistical significance of difference between device configuration is of similar importance.

5.2.1 Statistical Analysis of Primary Endpoint

5.2.1.1 Indwell Time

It is hypothesized that:

- PIVC indwell time will be greater for longer catheters
- PIVC indwell time will be greater for catheters of smaller gauge (larger bore)

In order to test these hypotheses, catheter indwell time will be assessed using survival analysis, including:

- Kaplan-Meier survival curves including Log-Rank test p-value
- Cox Proportional Hazards Model with Hazard Ratios for each device vs. default device condition (BD Nexiva 20G x 1 inch) and associated 95% Confidence Intervals. Effect of the following covariates will be investigated: gender, age, BMI and dominant arm.

Main analysis will be performed stratified by device, depending on the results pooled analyses by gauge or by catheter length might be performed. An example of the Kaplan-Meier curve and associated metrics is provided in Appendix B by Figure B.1.1. An example of the Hazard Ratios extracted from the Cox Proportional Hazards models is provided in Appendix A by Table A.4.2.

For the purpose of this survival analysis, device failure (inability to flush or draw blood, see section 6.6) will be identified as follows:

- Blood Draw: Variables DEBLDCS equal to “N” and DEBLDRS equal to “N” from table INBCINBC
- Flush: Variables DEFLSSU equal to “N” and DEFLSRS equal to “N” from table INFL

Failure can occur during any of the 7 repeats of the blood draw (for either tube volumes) or flush processes, as highlighted in orange on Table 2.7.1, for right or left arm, per randomization schedule. Date-time of failure is then given by the aggregation of variables DEDTN & DEFTM, from tables INBCINBC or INFL, respectively for blood draw or flush.

Additional Indwell Time summary statistics and graphical representation will be provided as represented in Appendix A by Table A.4.1 and in Appendix B by Figure B.2.1, respectively.

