4.2 Scientific Rationale for Study Design

Given that participant variability (e.g., coagulation and platelet function) may impact study endpoints (e.g., device indwell time and haemolysis)²³, the current study utilizes a simultaneous paired experimental design to assess whether differences in device design (i.e., lengths of 1 inch and 1.75 inch) impact PIVC indwell time; unpaired analysis will be employed to investigate the effects of catheter gauge on PIVC indwell time. PIVC length was selected for paired analysis as it is hypothesized that longer PIVC catheters may extend indwell time based upon catheter tip location within the vessel, increased tip distance from insertion site, and reduced probability of accidental dislodgement. Although gauge is a factor that may impact indwell time, participant screening is conducted to only enroll those with catheter-to-vessel (C/V) ratios no greater than 45%; thus it is anticipated that gauge will have an effect less susceptible to participant variability and was selected for the unpaired analysis. As both device length and gauge are expected to influence haemolysis^{17,20} the study design enables evaluation of both design features.

Identification of device design factors that improve PIVC indwell time and decrease incidence of haemolysis during PIVC-based blood collection is of clinical significance due to the associated benefits for the patient (e.g., uninterrupted medical treatment, and decreased discomfort, pain and anxiety)^{28,29,33}, for the health care worker (e.g., reduced chance of needle stick injuries)²⁸, and for the healthcare institution (i.e., reduced cost of care)^{12,29}.

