10.5 Primary Endpoint(s)

Comparisons across and between device configurations (i.e., length/gauge) will be made using logrank tests for indwell time. The primary endpoint will be evaluated using statistical modeling software (Prism, Release 8.3; GraphPad Software Inc., USA) or R (R 3.6.2 or higher).

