4.1 Population Definitions

In the unforeseen circumstance of a protocol deviation (e.g., 20G PIVC instead of 22G PIVC; blood was collected into 6mL vacutainer before 2mL for a specific participant), the data will be analyzed “as treated” - that is, data will be analyzed as the participant’s actual received intervention. However, in the unforeseen circumstance of a protocol deviation whereby a participant receives the wrong intervention (e.g., two different gauge catheters; two 20G catheters of the same length), they will be treated as per protocol (PP) and thus their data will be excluded from the study because paired comparison of catheter length will not be possible.

5 Statistical Analysis/Calculations

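### The length comparison is designed as paired, but the primary log-rank and Cox analysis names no method for two catheters in one participant and leaves the length and gauge contrasts optional

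*SAP*

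**What the plan says.** Protocol 4.2 gives the reason for the design: "Given that participant variability (e.g., coagulation and platelet function) may impact study endpoints (e.g., device indwell time and haemolysis"). It then states that "PIVC length was selected for paired analysis", while for gauge "unpaired analysis will be employed to investigate the effects of catheter gauge on PIVC indwell time". SAP 4.1 relies on the pairing as well. It excludes participants who receive the wrong combination of catheters "because paired comparison of catheter length will not be possible".

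The primary analysis is described in two places.

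- Protocol 10.5: "Comparisons across and between device configurations (i.e., length/gauge) will be made using logrank tests for indwell time".
- SAP 5.2.1.1 states two hypotheses, one on length and one on gauge. It lists "Kaplan-Meier survival curves including Log-Rank test p-value" and a "Cox Proportional Hazards Model with Hazard Ratios for each device vs. default device condition (BD Nexiva 20G x 1 inch"), with age, gender, dominant arm and BMI as covariates to be investigated. It adds: "Main analysis will be performed stratified by device, depending on the results pooled analyses by gauge or by catheter length might be performed".

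SAP 5.2.4 sets general modelling rules, among them removal of non-significant interactions, and says nothing on clustering. The secondary mixed models (SAP 5.2.2.1, 5.2.2.2 and 5.2.2.4) do name subject as a random effect.

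**The concern.** The two failure times from one participant share that person's coagulation, platelet function and behaviour. That is the Protocol's own reason for pairing. An analysis that treats 80 catheters as 80 independent units gets the standard errors wrong, and in opposite directions for the two hypotheses. Length is compared within participants, so ignoring positive correlation overstates its variance. Gauge is compared between participants, so pooling both catheters of each person understates its variance.

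Also, the contrasts that match the hypotheses are not fixed in advance. Protocol 10.5 states length/gauge comparisons without condition, whereas SAP 5.2.1.1 lets the data decide whether pooled ones are made. With 20G x 1 inch as reference, one of the three hazard ratios (22G x 1.75 inch) mixes gauge and length, and the length effect within 22G is not reported directly.

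At stake is the reading of a study meant to inform product development (Protocol 4.1). Its indwell analysis goes to business decision makers before database lock (SAP 2.6), and SAP 5.2 weights estimation about equally with significance.

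**Working it through.** **1. The plan's own power figure.** SAP 2.4 takes medians of 1 and 3 days, 3 days of follow-up, no loss, 19 and 20 units, and two-sided 0.05. Under exponential survival the event probabilities are 1 − 0.5³ = 0.875 and 1 − 0.5 = 0.500.

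- Expected events: 19 × 0.875 + 20 × 0.500 = 26.625.
- Schoenfeld: √(26.625 × (19/39) × (20/39)) × ln 3 − 1.96 = 2.833 − 1.960 = 0.873, so power is 0.809.
- A Lakatos-type calculation gives 0.806. The SAP states 0.8054.

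The figure reproduces as a comparison of two independent groups, so the sample size ignores the pairing too.

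**2. Direction of the error.** For two measurements with variance σ² and correlation ρ, the within-person difference has variance 2σ²(1 − ρ) and the within-person mean has variance σ²(1 + ρ)/2. Assuming independence gives 2σ² and σ²/2. For ρ > 0 the first is too large (length) and the second too small (gauge).

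**3. Size.** Assumptions: Gaussian copula with ρ = 0.2 / 0.4 / 0.6, exponential margins, 20 participants per gauge with two catheters each, failures detected at the seven scheduled access times, censoring at 72 h, 10,000 trials. The null median of 36 h and the 36 vs 72 h alternative are assumptions; 24 vs 72 h is the SAP's effect. Clustered means participant-clustered score variance × G/(G − 1), where G is the number of participants.

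| Quantity | Unadjusted | Clustered |
|---|---|---|
| Length, 20 pairs, null rejection | 3.2 / 1.9 / 0.6% | 4.5 / 4.4 / 3.7% |
| Length, 20 pairs, power at 24 vs 72 h | 83 / 86 / 87% | 85 / 91 / 96% |
| Length, 20 pairs, power at 36 vs 72 h | 40 / 38 / 38% | 41 / 49 / 59% |
| Length, 40 pairs, power at 36 vs 72 h | 70 / 71 / 74% | 73 / 81 / 91% |
| Gauge pooled over length, type I error | 7.0 / 9.1 / 11.0% | 5.4 / 5.5 / 5.1% |

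At ρ = 0 the unadjusted tests reject 5.1% (length) and 5.0% (pooled gauge). A separate run of 3,000 trials gave 4.5 / 1.9 / 0.5% for the length null and 7.5 / 10.3 / 11.7% for pooled gauge. In that run the clustered gauge test rejected 6.0 / 6.6 / 5.5% with a 1.96 cut-off and 5.0 / 5.7 / 4.8% with a t quantile.

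**4. Cross-check from standard errors.** In the Cox model with gauge, length and interaction, the null model-based SE is 0.261 for both overall length and average gauge. The true SDs are 0.241 / 0.215 / 0.187 for length and 0.285 / 0.306 / 0.321 for gauge. The implied rejection rate is 2Φ(−1.96 × SE/SD).

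- Length: SE/SD = 1.083 / 1.214 / 1.396, giving 3.4 / 1.7 / 0.6%.
- Gauge: SE/SD = 0.916 / 0.853 / 0.813, giving 7.3 / 9.5 / 11.1%.

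These agree with the simulated coverage of the unadjusted intervals: 96.8 / 98.4 / 99.3% for length and 92.9 / 90.9 / 89.2% for gauge. The unadjusted overall length CI is 5 / 17 / 37% wider than the clustered one.

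**5. Another dependence model.** With gamma frailty at Kendall's τ = 0.2 / 0.4, the unadjusted tests reject 2.2 / 0.3% (length, 20 pairs) and 9.5 / 13.8% (pooled gauge). For scale, Gaussian ρ = 0.6 corresponds to τ = (2/π) arcsin 0.6 = 0.41. The directions are the same, and the sizes depend on the model.

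**6. What is not affected.** An unadjusted four-group log-rank over the device configurations rejects 5.1 / 4.8 / 4.5 / 4.1% at ρ = 0 / 0.2 / 0.4 / 0.6 (4,000 trials). The by-device gauge contrast at 1 inch rejects 4.8–5.0%.

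**The case against.** Much of the case on the other side stands. The correlation is assumed. For length the error adds no false positives, and power at the planned effect is at or above the planned 80.5%; the material loss appears at 36 vs 72 h, an effect chosen for illustration. The study is a feasibility study with no acceptance criteria (SAP 2.9). The natural reading of the main log-rank is one four-group test, which keeps close to its level. The 40-pair length and pooled-gauge log-rank rows apply only if pooling is done.

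A reader might infer more than the documents support:

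- *That the paired design was abandoned.* Neither document says so. A method is unnamed, and an analyst could still add one.
- *That Protocol 10.5 and SAP 5.2.1.1 contradict each other on estimation.* Protocol 10.5 names no estimator. SAP 5.2.2.2 explains device configuration as gauge, length and their interaction, and a four-level device factor is that same model, so the reference in SAP 5.2.2.3 to gauge and length can be reconciled with it. The real difference is unconditional versus results-dependent comparisons.
- *That the 22G length effect cannot be estimated.* The fitted model yields it with a CI; it is only not listed for reporting.
- *That the different reference device in Table A.4.2 (22G x 1 inch) is an analysis conflict.* The table is an example, so this is editorial.
- *That only an optional pooled gauge test can be anti-conservative.* If SAP 5.2.4 removes a non-significant interaction, the Cox gauge term is itself pooled over length and has the same problem.

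**Conclusion.** The point holds and should be fixed. The plan relies on pairing but names no primary method that respects it, and the contrasts matching its two hypotheses depend on the results. If a participant's two catheters tend to fail together (ρ 0.2–0.6 assumed), the unadjusted length test rejects about 3–4.5% falling to below 1% under the null, and its interval is too wide. At an assumed 36 vs 72 h with 40 pairs, power is about 70–74% where clustering gives 73–91%. Any gauge estimate pooled over length has type I error of about 7–12% under the Gaussian copula, and somewhat more under gamma frailty. The planned 24 vs 72 h effect keeps more than 80% power, and at zero correlation there is no distortion. The consequence is imprecise or overconfident estimates in a feasibility study, not an invalid trial.

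**What to change.** In SAP 5.2.1.1:

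1. Remove the condition that makes pooling depend on the results. Name four contrasts: length overall, length within 20G, length within 22G, and gauge overall.
2. Take them from one Cox model with gauge, length and gauge x length, all kept whatever their p-values as a stated exception to SAP 5.2.4. Use participant-clustered robust variance × G/(G − 1) and t-based CIs: 19 df within a gauge (G = 20), 38 df overall (G = 40).
3. Take p-values from the matching participant-clustered log-rank tests with the same factor, and state the reference distribution. Use t with 38 df for overall gauge, where 1.96 is slightly liberal.
4. Put the listed covariates in a supportive adjusted model, and say whether the multiplicity adjustment in SAP 5.2.4 applies to the four contrasts.
5. Keep the four-device Kaplan-Meier curves and hazard ratios as description. As an editorial point, use one reference device in the text and Table A.4.2.

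A shared frailty or participant strata would also respect the pair. Clustering is preferable because one model serves both hypotheses. Participant strata cannot estimate gauge, which does not vary within a person. They also cost power for length: in the gamma-frailty runs with 20 pairs and the planned effect, 59% against 80% for clustering (without the G/(G − 1) factor) at τ = 0, and 85% against 97% at τ = 0.4.

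The cost is SAP wording and a cluster term, with no new data. The gauge CI becomes about 12 / 20 / 27% wider at ρ = 0.2 / 0.4 / 0.6. If the true correlation is zero, the length CIs are about 4% (overall) to 8% (within gauge) wider. About 2–4 points of length power are then lost with normal-reference p-values (for example 79% vs 81% with 20 pairs at 24 vs 72 h).

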2.7 Study Procedure

The time-windows for collection of the primary, secondary and exploratory endpoints are detailed in Table 2.7.1.

The primary endpoint data (catheter dwell time) and exploratory endpoint data (PIVC complications) will be collected over 7 time-windows (see text highlighted in orange on Table 2.7.1). The secondary endpoint data (cfHb, blood draw time) will be collected over 8 discrete timepoints (including baseline, see text highlighted in red on Table 2.7.1).

All other secondary endpoint data (e.g., blood flow velocity, vessel diameter), except incidence of extravenous thrombus (assessed once the catheter is removed), will be collected over 15 timepoints (see text

highlighted in blue and grey on Table 2.7.1). Please note that the cells that indicate ‘Day’ in Table 1 are indicating the interventional visit days and are not inclusive of the screening visit or follow-up visit.

The flush pressure profile exploratory endpoint data will be collected over 7 timepoints (see text highlighted in blue on Table 2.7.1).

Table 2.7.1: List of sampling time points for primary, secondary, and exploratory endpoints. cfHb: cell-free hemoglobin; TIP: catheter tip position; BFV: blood flow velocity; C/V: catheter to vein ratio; PRES: in vivo pressure; PIVC: peripheral intravenous catheter; FILL: blood draw fill time. Time T+00:00 is the time of insertion

Day	Visit	Timepoint code	Approximate (hh:mm)	Time	Measurements taken
Day 1	Baseline	D1.1	T-00:60		TIP, BFV, C/V via ultrasound (no indwelling catheter)
		D1.2	T-00:40		cfHb via venipuncture
	Morning	D1.3	T+00:15		TIP, BFV, C/V via ultrasound, PRES via PIVC during flush
		D1.4	T+00:25		cfHb, FILL via PIVC
	Afternoon	D1.5	T+00:35		TIP, BFV, C/V via ultrasound
		D1.6	T+06:00		TIP, BFV, C/V via ultrasound, PRES via PIVC during flush
		D1.7	T+06:15		cfHb, FILL via PIVC
		D1.8	T+06:25		TIP, BFV, C/V via ultrasound
Day 2	Morning	D2.1	T+24:00		TIP, BFV, C/V via ultrasound, PRES via PIVC during flush
		D2.2	T+24:15		cfHb, FILL via PIVC
	Afternoon	D2.3	T+24:25		TIP, BFV, C/V via ultrasound
		D2.4	T+30:00		TIP, BFV, C/V via ultrasound, PRES via PIVC during flush
		D2.5	T+30:15		cfHb, FILL via PIVC
		D2.6	T+30:25		TIP, BFV, C/V via ultrasound
Day 3	Morning	D3.1	T+48:00		TIP, BFV, C/V via ultrasound, PRES via PIVC during flush
		D3.2	T+48:15		cfHb, FILL via PIVC
	Afternoon	D3.3	T+48:25		TIP, BFV, C/V via ultrasound
		D3.4	T+54:00		TIP, BFV, C/V via ultrasound, PRES via PIVC during flush

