5.2.4 General Considerations

- For categorical data, count and percentage with 95% confidence interval will be calculated.
- For continuous data, average, standard error, 95% confidence interval, median, inter-quartiles, minimum and maximum will be provided.
- p-values less than 0.05 will be considered statistically significant. Multiple comparisons adjustments (Tukey's or Sydak's) will be made when appropriate
- Importance of factors/variables might be evaluated using machine learning tools such as the Boruta algorithm (random forest all-relevant approach)

- Whenever possible, effects of the following covariates will be investigated: gender, age and BMI
- Initially, all factors/variables will be included into the model as well as any two-way/three-way interactions.
- Variables or interactions which are not significant ($p\text{-value} < 0.05$) will be removed from the final model. Models adjusted with significant effects (and significant interactions if any) will be used for analysis whenever possible.
- Use of models will be preferred to non-parametric tests whenever possible.
- Residual plots for each model will be drawn and reviewed to ensure there are no systematic patterns.
- Transformation of response and/or explanatory variables will be investigated whenever modeling assumptions are not satisfied.

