6.2.2 Minor deviations

- **Incorrect order for collection of blood:** The order in which blood is collected into two alternate size vacutainers (2mL and 6 mL) will be randomized. In the unanticipated circumstance whereby the order of blood collection is incorrect, the data will be included and analyzed “as treated”.
- **Incorrect order for PIVC insertion:** The order in which the PIVCs are inserted into the arm will be randomized. In the unanticipated circumstance whereby the order of PIVC insertion is incorrect, the data will be included and analyzed “as treated”.
- **Incorrect allocation of PIVC length:** The alternate PIVC lengths will be randomized to the participants arms. In the unanticipated circumstance whereby allocation of PIVC length is incorrect (e.g., the 20G 1.0 inch PIVC is inserted into the participant’s right arm when it was intended for the participant’s left arm), the data will be included and analyzed “as treated”.

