6.3 Demographics and Baseline Variables

Demographic variables will include all medical history questionnaire responses, and each of the following variables at time of intervention:

- Age
- Height
- Weight
- Resting blood pressure
- Gender
- BMI
- Menstrual cycle phase (women only)

Table A.1.1 provides an example of demographic variables summary table, per study group and overall.

Baseline variables will include all sonographic data prior to PIVC insertion and cfHb collected via

venipuncture. Tables A.3.1 and A.3.2 provide examples of baseline variables summary table, per study group and overall, including blood analysis.

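### The primary indwell-time model does not prespecify adjustment for pre-insertion vein diameter, so the 20 v 20 gauge comparison gives up precision and is exposed to chance imbalance

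*SAP*

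**What the plan says.** - **Primary analysis.** Protocol 10.5: "Comparisons across and between device configurations (i.e., length/gauge) will be made using logrank tests for indwell time". SAP 5.2.1.1 adds a Cox model with hazard ratios against the 20G x 1 inch device. On covariates it says: "Effect of the following covariates will be investigated: gender, age, BMI and dominant arm". The main analysis is by device; pooling by gauge or by length is optional.
- **Retention.** Under SAP 5.2.4, terms that are not significant "will be removed from the final model". The four named covariates are therefore candidates, not fixed adjustments.
- **Gauge contrast.** Protocol 4.2: "unpaired analysis will be employed to investigate the effects of catheter gauge on PIVC indwell time". Protocol 8.3 aims for at least 20 completers per gauge.
- **Vein size at entry.** Protocol 4.2: "participant screening is conducted to only enroll those with catheter-to-vessel (C/V) ratios no greater than 45" (per cent). Protocol 5.1 and 5.2 turn this into a minimum diameter of about 2.55 mm. No upper limit is set, and no stratification by vein size is described.
- **Vein size as data.** SAP Table 2.7.1 schedules at D1.1, an hour before insertion, "TIP, BFV, C/V via ultrasound (no indwelling catheter"). SAP 6.3: "Baseline variables will include all sonographic data prior to PIVC insertion". Protocol 7.2 has both arms scanned.
- **Vein size in analysis.** Protocol 10.6 lists vessel dimension among predictors in secondary models of indwell time and 72-hour failure. SAP 5.2.2.3 lists C/V ratio in a Boruta survival-forest ranking.
- **Insertion order.** SAP 6.2.2: "The order in which the PIVCs are inserted into the arm will be randomized". Under SAP 2.3.1 each participant receives both lengths of one gauge, one in each arm.

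**The concern.** The length comparison is made within a person, so most person-level variation cancels. The gauge comparison is made between about 20 people and another 20, and nothing cancels. Protocol 4.2 accepts this on the ground that screening on C/V ratio makes the gauge effect less sensitive to differences between people. A floor, however, removes only the small veins; diameters above it can still vary and can differ by chance between the gauge groups.

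If vein diameter predicts failure, an unadjusted Cox model pays in two ways. In a given trial, a chance difference in vein size shifts the gauge hazard ratio. Over repeated trials, power is lower and the estimated hazard ratio lies closer to 1 than the ratio at a given vein size. SAP 5.2 gives estimation and significance similar weight, so both matter. The secondary analyses do not fill the gap: an importance ranking gives no adjusted gauge hazard ratio.

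**Working it through.** **1. The plan's own power figure.** Inputs from SAP 2.4: 19 and 20 catheters, medians of 1 and 3 days, 3 days' follow-up, no loss, two-sided alpha 0.05, hazard ratio 0.3333.

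- Expected events: 19 x (1 - 0.5^3) + 20 x (1 - 0.5) = 16.6 + 10 = 26.6.
- Schoenfeld: sqrt(26.6 x 19/39 x 20/39) x ln 3 - 1.96 = 0.87, so power is 0.809. A Lakatos-type calculation gives 0.806.
- Stated power is 0.8054, so the design inputs are reproduced.

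**2. Chance imbalance in vein diameter.** With 20 per gauge, one vein each and simple randomisation, the SD of the difference in means is sqrt(2/20) = 0.316 SD.

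- P(difference above 0.3 SD) = 34%; P(above 0.5 SD) = 11%.
- If the hazard changes 1.5-fold per SD (assumed), the 95% limit of the resulting shift in hazard ratio is exp(ln 1.5 x 0.316 x 1.96) = 1.29-fold. At 2-fold per SD (assumed) it is exp(ln 2 x 0.316 x 1.96) = 1.54-fold.
- Pooling both arms with a between-arm correlation of 0.5 (assumed) narrows these to about 1.24 and 1.45.

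**3. Power and estimate with and without adjustment.** I simulated 4,000 trials per setting: 20 v 20 catheters of one length, exponential times, reference median 1 day, cut at 3 days, and a standard-normal vein covariate. Its strength is not in the documents and is varied from nil to strong. The hazard ratio at a given vein size is 1/3.

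| log HR per SD (assumed) | Power, unadjusted | Power, adjusted | Median HR, unadjusted | Median HR, adjusted |
|---|---|---|---|---|
| 0 | 0.81 | 0.81 | 0.33 | 0.32 |
| 0.25 | 0.78 | 0.80 | 0.34 | 0.32 |
| 0.5 | 0.71 | 0.78 | 0.37 | 0.33 |
| 0.75 | 0.61 | 0.78 | 0.40 | 0.32 |
| 1.0 | 0.52 | 0.78 | 0.44 | 0.32 |

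The loss runs from 0 to about 25 points. At a smaller gauge effect (hazard ratio 0.5) it runs from 0 (0.47 v 0.47) to about 19 points (0.24 v 0.43).

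**4. Type I error.** With no gauge effect the unadjusted model rejects in 0.047 to 0.056 of trials and the adjusted model in 0.050 to 0.058.

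**5. Why diameter and not C/V ratio.** SAP 5.1.5 takes the numerator from the device specification: 0.90 mm for 22G and 1.10 mm for 20G. The same 2.55 mm vein has a C/V of 0.90/2.55 = 35% with 22G and 1.10/2.55 = 43% with 20G. Holding C/V fixed compares a 20G catheter with a 22G catheter in a vein 0.90/1.10 = 0.82 times as wide, which is a different question.

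**6. Room for the covariate.** If half of the 80 catheters fail at each of the plan's two rates, expected events are 80 x (0.875 + 0.5)/2 = 55.

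**7. Insertion order.** Each participant contributes one first and one second catheter of the same gauge, so the correlation of order with gauge in the pooled data is exactly 0. With an assumed order effect of log HR 0.5, adding order moves pooled power from 0.988 to 0.991, or from 0.890 to 0.897 with an assumed participant frailty SD of 0.7. Imbalance can arise only in single-length contrasts: under simple randomisation a difference of 4 or more first placements has probability 27%, and of 6 or more, 8%. The dummy list in SAP Table C.0.1 shows all eight gauge, arm and first-length codes once in each of its first two runs of eight. If the real list is blocked in that way, this largely disappears too.

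**The case against.** The best case for the plan is that gauge is randomised, the unadjusted test keeps its size, and this is a feasibility study with no acceptance criteria. Vein size is also examined against indwell time in the secondary analyses, and the power gain depends wholly on an association the documents do not report. All of that stands. A further practical point also stands: SAP 5.1.5 derives vessel diameter from scans with the catheter in view, and the dummy baseline listing holds one C/V value per participant, so a per-arm pre-insertion diameter needs its own derivation rule.

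It can also be said that gauge and C/V together carry the vein-diameter information. That is true for prediction, but it does not give a clean gauge hazard ratio (step 5).

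Several stronger readings are tempting and are not supported:

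- A reader might infer that the gauge test is invalid or biased without vein diameter. It is not. Chance imbalance is already part of the sampling error, and the pull of the hazard ratio towards 1 reflects averaging over vein sizes, not confounding.
- A reader might infer that leaving out insertion order exposes the pooled gauge comparison in the same way. The within-participant balance rules that out.
- A reader might infer that the plan adjusts for gender, age, BMI and dominant arm. It only investigates them.
- A reader might infer that the protocol names vessel size as the chief person-level influence on the gauge effect. Protocol 4.2 gives coagulation and platelet function as its examples, and cites C/V screening as a reason to expect less sensitivity.

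**Conclusion.** The point holds as one of efficiency and chance imbalance. The primary model has no prespecified adjustment for a baseline measurement that is scheduled before insertion, bounded at entry only from below, and treated by the plan itself as a candidate predictor of indwell time.

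Under the plan's hazard ratio of 1/3 with 20 v 20 catheters, leaving it out costs between 0 and about 25 points of power and moves the estimated hazard ratio from 0.33 to as far as 0.44. The range rests on the assumed prognostic strength (log HR 0 to 1.0 per SD), exponential failure times and a normal covariate; the documents cannot narrow it. At the zero end, adjustment costs essentially nothing, so the change has little downside even if vein size proves unimportant.

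**What to change.** Add to SAP 5.2.1.1 that the primary Cox model includes the pre-insertion diameter of the cannulated cephalic vein (mm, continuous, from the D1.1 scan, one value per arm) as a fixed covariate, exempt from the removal rule in SAP 5.2.4. State that C/V ratio is not used for this purpose. Keep the unadjusted log-rank test and report it alongside.

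Add a derivation rule for the D1.1 diameter to SAP 5.1.5, and list it per arm in the baseline tables. SAP 5.2.5 does not impute, so a missing D1.1 scan would remove that catheter from the adjusted model only; report how many are affected.

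Insertion order (first or second) may optionally be added for the length and single-length device contrasts. It is not needed for the pooled gauge comparison.

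The cost is SAP wording, one parameter against about 55 expected events, and the small derivation step. It should be settled before the preliminary indwell-time analysis in SAP 2.6, so that the choice cannot look data-driven.
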